7.1 Adherence & Satisfaction Assessments

The following assessments will be made to assess the adherence and satisfaction with anticoagulants after cystectomy (corresponding to primary and secondary objectives in section 3):

- 1. Medication counting—study personnel will assist with medication counting over the phone. This involves the participant counting the pills/vials of medication they have remaining and then the study personnel will use the date of surgery, date of discharge, and size of prescription found in the medical record to calculate the **proportion of days covered (PDC)**. PDC is the primary endpoint of the study and is the most objective measure of adherence.
- 2. National Institute of Health (NIH) Patient-Reported Outcomes Measurement Information System (PROMIS) Medication Adherence Scale (PMAS)^{29,30} this questionnaire is a validated, nine-item, patient-reported measure of medication adherence that can be either administered by study personnel over the phone or filled out directly in RedCap by study participants who elect to have a secure weblink emailed to them.
- **3.** Patient Satisfaction study personnel will ask a series of independent questions over the phone or participants will answer them directly in RedCap if they elect to have a secure weblink emailed to them. These questions elucidate possible reasons for compliance/noncompliance that are hypothesized specifically to apply to enoxaparin and apixaban.

7.2 Cost Assessments

The following assessments will be made to assess the cost of anticoagulants when used as EP (corresponding to secondary objectives in section 3).

- 1. **COST-FACIT** this is a 12-item questionnaire developed and validated in the cancer population for assessing patient-reported financial distress due to healthcare costs that can be either administered by study personnel over the phone or filled out directly in RedCap by study participants who elect to have a secure weblink emailed to them.
- 2. The total cost, amount paid by insurance, and patient out of pocket cost for each anticoagulant (in dollars) will be tracked by the inpatient pharmacy. This is collected via electronic review of pharmacy records.

7.3 Assessing Covariates

- 1. **Demographics Questionnaire** this questionnaire is administered by study personnel either in person, over the phone, or filled out directly in RedCap by study participants who elect to have a secure weblink emailed to them. Some chart review may be performed to assist in completion. It will collect variables to help evaluate what sociodemographic covariates may be influencing study endpoints.
 - a. The Demographics Questionnaire we include the **modified**, **5-item Frailty Index**. ²⁹ Initially developed a an 11-item index, the Frailty Index was developed using NSQIP comorbidities and then shortened to a 5-item index that has been shown to predict complications, discharge destination, and healthcare utilization after radical cystectomy. ^{30,31}
- 2. In addition to these discrete questionnaires, **chart review** will be performed ascertain what **perioperative variables** may be influencing study endpoints:
 - a. Length of surgery
 - b. Surgical approach (robotic vs open)
 - c. Type of diversion (ileal conduit, catheterizable channel, or neobladder)
 - d. Number of blood transfusions both intraop and periop (in units)
 - e. Length of stay (in days)

7.4 Drug Efficacy & Safety Assessments

In order to achieve the tertiary objective of collecting data regarding the efficacy and safety of both enoxaparin and apixaban when used as EP in the setting of radical cystectomy, we will directly enquire about instances of VTE and instances of bleeding. Screening questions for VTE and bleeding will be performed by study personnel and any positive screen will trigger review by one of the investigators, including review of the participant's medical record for results of imaging, labwork, notes from ED visits or inpatient admissions, or any other information deemed necessary by the investigator to confirm presence of VTE or bleeding and describe the outcome. This review will be conducted in accordance with HIPPA regulation. Review of the VTE or bleeding event will be performed for study documentation purposes; participants will be referred to their treating clinician for management of the VTE or bleeding, or if deemed necessary by the PI, to the emergency department for expedited care and their treating clinician notified of this for continued management.

7.4.1 Assessing VTE

VTE will be categorized as DVT, PE, or both. To asses for VTE, all participants will be directly asked if they have been diagnosed with a blood clot. A positive screen will be reported to the investigators who will review the event as described above,

Development of VTE may result in the patient being discontinued from the study intervention (because they will likely no longer be on prophylactic dose of anticoagulant, but rather therapeutic dose) but not discontinuation from the study.

7.4.2 Assessing Bleeding

Bleeding events will be categorized as Major, Clinically-Relevant Non-Major (CRNM), and Minor. Major events and CRNM are defined according to the International Society on Thrombosis and Haemostasis (ISTH) Subcommittee of Scientific and Standardization Committee.^{32,33} Minor bleeding is defined as clinically overt bleeding that does not meet criteria for Major or CRNM bleeding.

To assess for Major and CRNM bleeding, participants will be directly asked if they have had bleeding that resulted in presentation to ED, inpatient admission, transfusion, or procedural intervention. To assess for Minor bleeding (or bleeding that is Major/CRNM but not yet diagnosed) participants will be asked about bruising or any other bothersome bleeding. All positive screens for bleeding events will be reviewed by a trial investigator to ensure appropriate clinical classification as Major, CRNM, or Minor. A positive screen will be reported to the investigators who will review the event as described above

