4.1 Minimizing Bias

Patients will be randomized to a prescription for one of the two anticoagulants at the time of postoperative discharge, and instructed to continue the medication until POD30. Randomization will be performed in a simple 1:1 fashion.

The randomization will be non-blinded. Given that this trial aims to explore the real experience of patients on these medications, blinding and placebo would actually detract from the important clinical context and understanding that participants have. Furthermore, enoxaparin and apixaban have different routes of administration (enoxaparin is injectable and apixaban is oral) which makes blinding and placebo infeasible. Blinding of the investigators is not necessary given the outcomes are patient reported surveys and pill/vial counts. Bias will be sufficiently reduced by randomization.

The University of Pennsylvania will serve as the primary site, and Vanderbilt University Medical Center as a second site. The addition of a second site will also introduce variety into the study population and strengthen its applicability.

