9.6 Analysis of Safety Endpoints

Given the well-established safety profile of both drugs and their use as SOC after cystectomy there is no formal safety endpoint for this study. However, both bleeding and VTE events will be solicited and tracked (see section 7) for safety analysis. DVT, PE, and a composite

outcome of the two will be compared between the two study arms using a test of proportions. For bleeding events, medical review of the chart by an investigator will determine if the event is Major, Clinically Relevant Non-Major (CRNM), or Minor (see section 7) and these three outcomes will be compared between the two groups as well as a composite outcome of Non-Minor Bleeding (Major and CRNM) using test of proportions.

These as well as any other adverse events will be graded (see section 7) and presented in a descriptive way with any further detail deemed clinically relevant by the PI (including but not limited to the treatment and outcome of the AE) included.

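### Minor bleeding is screened by asking about bruising and tested between an injected and an oral drug, but the plan does not separate injection-site bruises

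*Combined protocol and SAP*

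**What the plan says.** Section 7.4.2 sets the screen for Minor bleeding: "participants will be asked about bruising or any other bothersome bleeding". The class itself is residual: "Minor bleeding is defined as clinically overt bleeding that does not meet criteria for Major or CRNM bleeding". A positive answer is not yet an event, because "All positive screens for bleeding events will be reviewed by a trial investigator to ensure appropriate clinical classification as Major, CRNM, or Minor". Section 7.4 adds that the reviewer may use the medical record to confirm that bleeding occurred. None of this text refers to the site or cause of a bruise.

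Section 9.6 takes Major, CRNM and Minor bleeding and says "these three outcomes will be compared between the two groups", by a test of proportions. It adds a composite of Major and CRNM. Section 9.1 makes all tests two-sided at 0.05. Section 9.7 runs the safety analyses in the ITT set and again in participants classed as adherent.

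Section 4.1 records that "enoxaparin is injectable and apixaban is oral" and that "The randomization will be non-blinded". On the standing of these outcomes, section 3 lists bleeding as tertiary and section 9.6 says "there is no formal safety endpoint for this study". The synopsis (objective 4) gives the purpose of collecting them: to add to existing studies for a possible meta-analysis.

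**The concern.** The question is worded identically for both arms but does not pick up the same things in each. Someone injecting daily at home can bruise where the needle went in. Someone taking tablets has no such site. Because Minor is whatever overt bleeding falls below CRNM, and bruising is the first thing asked about, these bruises have an open path into the count that 9.6 tests.

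What is at stake is interpretation. A reader who sees more Minor bleeding on enoxaparin could not tell whether it reflects the needle or bleeding elsewhere. The mixing runs in one direction, against the injected drug. The same ambiguity would pass into any meta-analysis that takes the Minor count, and nothing in the plan requires the bruise site to be recorded so that the count could be split afterwards. The adherent-only safety analysis sharpens the issue, since its enoxaparin members are those who took every intended dose.

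**Working it through.** The plan states no rate of Minor bleeding, no bruise rate and no power for this comparison, so there is no figure to reproduce. The calculation below only illustrates how much the missing separation could matter.

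**Inputs from the documents**
- 45 analysable participants per arm (section 9.3.1). The enrolment target of 108 (section 5.3) is 54 per arm if split evenly.
- Two-sided test at 0.05 (section 9.1), applied as a test of proportions to Minor bleeding (section 9.6).

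**Assumptions, not in the documents**
- b: the proportion with Minor bleeding other than injection-site bruising, equal in both arms.
- s: the proportion of the enoxaparin arm with an injection-site bruise, independent of b, always reported and always classified as Minor. The apixaban arm has none.

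**Formula**
Enoxaparin rate = 1 − (1 − b)(1 − s); apixaban rate = b. For example, b = 10% and s = 20% give 1 − 0.90 × 0.80 = 28% against 10%.

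The chance of p<0.05 was found by exact binomial enumeration of the pooled two-proportion z-test, 45 per arm:

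| s | b = 10%: rates | chance of p<0.05 | b = 20%: rates | chance of p<0.05 |
|---|---|---|---|---|
| 0% | 10% v 10% | 0.06 | 20% v 20% | 0.05 |
| 5% | 14.5% v 10% | 0.11 | 24% v 20% | 0.08 |
| 10% | 19% v 10% | 0.24 | 28% v 20% | 0.15 |
| 20% | 28% v 10% | 0.62 | 36% v 20% | 0.41 |
| 30% | 37% v 10% | 0.89 | 44% v 20% | 0.71 |
| 40% | 46% v 10% | 0.98 | 52% v 20% | 0.90 |

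Checks:
- A normal approximation gives 0.59 in place of 0.62 at b = 10%, s = 20%.
- At 54 per arm the exact figure for that cell is 0.69.
- With b = 5% and s = 20%, at 45 per arm, it is 0.78.
- If the review confirms only a fraction f of the bruises as Minor, s is replaced by f × s. With s = 20% and half confirmed, the relevant row is s = 10%, so 0.62 falls to 0.24.
- The s = 0 row is what the comparison without injection-site bruises would show: about 5% to 6%, the nominal level.

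The effect is small at bruise rates near 5% and large from about 20% upward.

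**The case against.** The strongest reply is that nothing here is an error. Section 4 calls the trial pragmatic, and section 4.1 says it is meant to capture what patients actually experience on each drug. A bruise caused by injecting the assigned drug is part of that experience. On this view the probabilities above are power to detect a true difference in Minor bleeding as defined. **This stands.** A reader might infer that the plan would produce false-positive results or a biased safety comparison. The documents do not support that, because no section says the target is bleeding apart from route. What remains is that a single total mixing two causes cannot be interpreted.

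Second, the bruising question is only a screen. An investigator must confirm overt bleeding and classify it, and may decline to count an injection-site bruise. **This stands in part.** Entry into Minor is likely but not certain, so the table is an upper case for each s. But the reviewer has no written rule on site, and the investigators are unblinded, so case-by-case decisions could themselves differ by arm.

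Third, it might be inferred that only the enoxaparin arm can have such bruises. That is too strong. Section 8.3 allows crossover before discharge while the safety analysis stays ITT, and bruises from any injections in hospital could appear in either arm. The one contraindication that section 8.3 anticipates (low creatinine clearance, for enoxaparin) moves participants from injections to tablets, which would dilute the effect.

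Fourth, section 9.6 lets the PI add descriptive detail, and the screening form is not in the documents and may already record site. Both are possible. The first is discretionary and the second cannot be checked.

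**Conclusion.** The point holds as a gap in definition and reporting. The plan tests Minor bleeding between an injected and an oral drug after prompting for bruising, and gives no rule for injection-site bruises. If these are classified as Minor, the result mixes route of administration with other anticoagulant bleeding.

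The size is unknown, because it depends on a bruise rate that the documents do not give. Across assumed rates of 5% to 40%, at 45 per arm and with every bruise counted, the chance of p<0.05 with no difference in other bleeding runs from about 11% to 98% at 10% background, and from about 8% to 90% at 20% background. Incomplete confirmation by the reviewer, or crossover away from injections, would lower these figures.

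The reach is limited to one tertiary outcome with no formal safety endpoint behind it. The primary endpoint does not use the bleeding data, and the Major-plus-CRNM composite leaves Minor events out. The change is worth making because it costs almost nothing now and bruise site would be hard to recover after the calls.

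**What to change.** 1. Add one item to the bleeding screen, asked in both arms: was the bruising only at an injection site (yes/no)?
2. In section 7.4.2, state that isolated injection-site bruising is coded as its own subcategory, in whichever arm it occurs, so that the reviewer follows a written rule.
3. In section 9.6, report the Minor-bleeding comparison both with and without that subcategory. Showing both keeps the patient's full experience in view. Making the comparison without these bruises the only one tested would set aside a real effect of the injected drug, and is not needed.

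Cost: one checkbox, one sentence in each of the two sections, and one extra line in the safety table. No treatment or clinical rule changes.

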8 SCREEN FAILURE, DISCONTINUATION, AND CROSSOVER

8.1 Screen Failures

Screen failures are defined as participants who agree to participate in the clinical trial but do not ultimately enroll. In order to comply with the Consolidated Standards of Reporting Trials (CONSORT) publishing requirements, all potential participants who are screen failures will complete a demographics form and the reason for their screen failure will be documented.

Participants who are screen failures due to a medical contraindication to enoxaparin or apixaban which then improves to meet the trial standard may be rescreened and will be assigned the same participant number as for the initial screening.

8.2 Discontinuation of Study Intervention, Discontinuation from Study

Prophylactic anticoagulation is standard of care after RC and therefore the decision to stop prophylaxis should be situated within a discussion with the treating clinician. The following are anticipated reasons participants may be told to discontinue study intervention (ie stop their anticoagulant) by their treating clinician:

- Development of blood clot. This would require discontinuation of prophylactic dose in favor of therapeutic dose and may involve switching anticoagulant type
- Development of bleeding event
- Development of an adverse event possibly related to the anticoagulant

- Development of a serious adverse event that would make prophylactic anticoagulation contraindicated

If study personnel discover any of these occurrences during study visits and they are not known already to the treating clinician, study personnel will refer the participant to their treating clinician for management, which may include consideration of discontinuation of the anticoagulant.

Study personnel will screen for discontinuation of the study intervention (ie discontinuation of the assigned anticoagulant) that has already occurred at the beginning of the POD30 and POD90 telephone calls. Any instances of study discontinuation will be brought to the attention of the PI and at the discretion of the PI participants who must discontinue the study intervention may remain in the study and complete portions of study visits depending on their reason for anticoagulant discontinuation and length of time they were following study protocol.

Participants may alternatively be discontinued completely from the study for the following reasons:

- Failure to undergo radical cystectomy and pelvic lymph node dissection
- Failure to be discharged on prophylactic anticoagulant
- Failure to be discharged by POD14
- Lost to Follow Up, defined as failing to complete the study visit despite three attempts to contact the participant via phone and/or email
- Participant request; participants are free to withdraw at any time

Any study discontinuation or discontinuation of the study intervention will be documented, including the date and reason for discontinuation. All instances will be reviewed by PI.. Participants who are discontinued will not be replaced.

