1.2 Schema

Screening participants by inclusion and exclusion criteria **Pre-operative** Obtaining informed consent, Enrolling participants **Clinic Visit Demographics Questionnaire** Surgery, Inpatient Recovery Randomization Apixaban Enoxaparin Discharge At home, self-administration of anticoagulant Phone Call #1: • Medication counting **POD 30** PROMIS, Patient Satisfaction Questionnaire (end of Chart review for perioperative variables & pharmacy prophylactic cost data anticoagulation) Screening for VTE & bleeding Phone Call #2: **POD 90** • COST Questionnaire Screening for VTE & bleeding

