3 STUDY OBJECTIVES AND ENDPOINTS

OBJECTIVES	ENDPOINTS	JUSTIFICATION FOR ENDPOINTS
Primary		
To compare rates of adherence to discharge on enoxaparin vs apixaban	Proportion of days covered (PDC). This will be calculated based on the size of prescription the patient was provided, day of surgery, day of discharge, and how many pills/syringes are remaining at POD30.	This is an objective and quantitative way to measure adherence.
Secondary		
To explore possible reasons for adherence vs non adherence	PROMIS Medication Adherence Scale: a nine-item questionnaire ^{26,27}	This is a validated measure of medication adherence that focuses on the possible reasons for non-adherence
	Participant satisfaction	Participants will answer questions specific to the use of enoxaparin and apixaban at home after RC. These questions were selected based on the clinical experience of the PIs as well as other studies that have examined adherence to enoxaparin and apixaban ^{21,27,28}
	COST-FACIT: a 12-item questionnaire ²	This is a questionnaire that was developed and validated in the cancer population for assessing patient-reported financial distress due to healthcare costs. This questionnaire adds a patient reported component, as simple cost data does not capture how burdensome that cost is to each specific patient
To compare the cost of enoxaparin vs apixaban	Out of pocket cost of prescription for anticoagulant, in dollars	This provides objective measure of the cost comparison between enoxaparin and apixaban. This data combined with adherence data may allow providers to determine the most cost effective option.

OBJECTIVES	ENDPOINTS	JUSTIFICATION FOR ENDPOINTS
Tertiary		
To collect mefficacy and safety data regarding both forms of prophylaxis	Rate of VTE, either PE or DVT Rate of bleeding events, classified as major, clinically relevant nonmajor, or nonmajor.	While data suggest VTE rates are comparable between enoxaparin and apixaban in both non-urologic and urologic studies, the urologic studies are in small populations. We therefore plan to track VTE and bleeding as outcomes to continue contributing to the pool of data. These outcomes would likely have been measured even if they were not outcomes as part of safety monitoring.

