7 STUDY ASSESSMENTS

At the time of enrollment, participants will be offered to complete the Demographics questionnaire either in person (if applicable), via phone (if applicable), or via a secure REDCap link emailed to them.

Participants will be contacted via phone on POD30 and POD90. During the phone call, participants will be given the option to receive an email with a secure link to REDCap to complete the majority of the study visit electronically (PMAS, Patient Satisfaction, and COST

questionnaires). Medication counting and screening for adverse events including VTE and bleeding must be done over the phone rather than via emailed link.

Study assessments will be conducted by staff other than the treating physician, and staff members will clearly state the contact is part of the research study, not part of routine clinical care.

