9.3 Analysis of the Primary Endpoint

The primary objective of this study is to compare drug adherence between the two study arms, and the corresponding primary endpoint of the study is the proportion of days at home during which the participant took the prescribed anticoagulant. This is defined as the proportion of days covered (PDC).

PDC = number of days of anticoagulant actually taken / number of days of anticoagulant supposed to take

Number of days of anticoagulant actually taken is determined during the POD 30 phone call by asking the participant how many pills/vials they have remaining and then subtracting that from the size of the prescription they were given. Number of days of anticoagulant supposed to take is calculated by subtracting the number of days postop the patient was discharged from 30.

PDC will be compared between the two groups using a **non-inferiority trial design** with difference in proportions test with the following hypothesis:

H₀: Apixaban is inferior to Enoxaparin in terms of the average PDC response.

HA: Apixaban is non-inferior to Enoxaparin in terms of the average PDC response.

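### The loss-to-follow-up rule in Section 8.2 permits a participant to be closed after three failed attempts by phone or email, so the POD30 medication count and the POD90 data may be lost avoidably

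*Combined protocol and SAP*

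**What the plan says.** All references are to the combined protocol and SAP.

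- **Section 8.2.** The list introduced by "Participants may alternatively be discontinued completely from the study for the following reasons" includes "Lost to Follow Up, defined as failing to complete the study visit despite three attempts to contact the participant via phone and/or email". The principal investigator reviews every instance, and "Participants who are discontinued will not be replaced". No number of phone attempts, spacing, visit window or later re-attempt is given. The same section lets people who stop the drug remain in the study at the principal investigator's discretion; it has no matching provision for people who miss a call.
- **Section 7.** "Participants will be contacted via phone on POD30 and POD90". Questionnaires may be completed through an emailed link, but "Medication counting and screening for adverse events including VTE and bleeding must be done over the phone rather than via emailed link".
- **Sections 1.2, 3 and 9.3.** The count belongs to the first call ("Phone Call #1: • Medication counting"). The endpoint rests on "how many pills/syringes are remaining at POD30", and the number of days taken "is determined during the POD 30 phone call by asking the participant how many pills/vials they have remaining".
- **Sections 1.2 and 4.** The POD90 call carries the COST questionnaire and the VTE and bleeding screen. No make-up count is listed.
- **Section 6.** Self-administration runs through POD30.
- **Section 9.7.** Missing data are taken as random and left out of all analyses. The primary analysis is labelled intention-to-treat in all randomized participants.

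**The concern.** The closing rule and the data-collection rule do not fit together. The primary endpoint can be obtained only by phone, yet the attempts that justify closing a participant need not be phone calls. The count has one scheduled occasion, and the rule offers an exit at that occasion although a second phone contact is already planned.

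The endpoint is adherence, so being hard to reach around POD30 is plausibly related to it: people who are readmitted, unwell or disengaged may have taken their anticoagulant differently. If they are closed at POD30, the trial loses their PDC and also the POD90 COST, VTE and bleeding data, which Section 1.1 says are collected for possible meta-analysis. Dropping missing values as random cannot repair such a loss, whereas collecting the data can.

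**Working it through.** **1. The rules side by side.** Mode of attempt that counts toward closure: phone and/or email (8.2). Mode that can yield the primary endpoint: phone only (7). Consequence: possible complete discontinuation, reviewed by the principal investigator, without replacement (8.2). Second phone contact: POD90, with no count (1.2, 4). Treatment of a missing PDC: dropped (9.7). Taken literally, three unanswered emails satisfy the definition.

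**2. What the plan's own figures give.** Section 5.3 enrols 108 to analyse 90: 108 − 90 = 18, and 18/108 = 16.7%. This allowance is not broken down. Consent is preoperative, so it also covers no cystectomy, no prescription and discharge after POD14. The share due to missed calls is not stated.

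The stated 45 per arm (Section 9.3.1: 85% control, 15-point margin, one-sided 0.05, 80% power) does not reproduce with the usual binary formula at equal true rates: (1.645 + 0.842)² × 2 × 0.85 × 0.15 / 0.15² = 70.1, so 71 per arm. It does reproduce for a mean PDC with SD of about 0.286, a value that the plan does not state. That is a separate matter, and this point does not depend on it. Both versions are carried below.

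**3. Upper bound on power.** Suppose all 18 losses were missed POD30 counts. Recovering 0%, 50% or 100% gives 90/2 = 45, 99/2 = 49.5 or 108/2 = 54 per arm.

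- Mean: power = Φ(0.15 / (0.286 × √(2/n)) − 1.645).
- Binary: power = Φ(0.15 / √(2 × 0.85 × 0.15 / n) − 1.645).

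| n per arm | Mean, SD 0.286 (assumed) | Binary, 85% in both arms |
|---|---|---|
| 45 | 80.0% | 63.6% |
| 49.5 | 83.3% | 67.2% |
| 54 | 86.0% | 70.5% |

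The most that could be gained is 6 to 7 points. With only 5 losses (51.5 per arm), full recovery moves power from 84.5% to 86.0%, or from 68.7% to 70.5%, which is under 2 points. Power is not the main argument.

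**4. Bias (assumed inputs).** Let fA and fE be the fractions missing on apixaban and enoxaparin, let responders in both arms have PDC 0.85, and let missing participants have PDC m. The observed difference is 0. The true difference is (fE − fA) × (0.85 − m). With fA = 0.22 and fE = 0.11:

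- m = 0.3: −0.11 × 0.55 = −0.0605, about −6 points.
- m = 0.5: −0.11 × 0.35 = −0.0385, about −4 points.
- m = 0.7: −0.11 × 0.15 = −0.0165, about −2 points.

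Reversing the arms reverses the sign. Equal missingness with the same m in both arms gives no bias in the difference.

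**5. Worth of a late count.** PDC counts as taken whatever has left the stock. A day's supply discarded, or used after POD30, therefore adds 1/(30 − discharge day) to that participant's PDC. For discharge at POD5 (assumed), 1/25 = 4.0 points. At POD14, the latest allowed by Section 5.2, 1/16 = 6.25 points. The error goes one way, towards higher adherence.

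**The case against.** Four objections have force.

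- **Phone is already the contact mode.** Section 7 has participants phoned at both time points and offers the emailed link during the call. Email in Section 8.2 can be read as a way to arrange the call or chase questionnaires. A reader might infer that the protocol directs staff to close people after three emails. It does not: doing so would mean not following Section 7. What stands is that the definition, as worded, would still be met.
- **Closure is neither automatic nor tied to POD30.** Section 8.2 is permissive, requires review by the principal investigator and speaks of the study visit without naming which. A reader might infer that a missed POD30 call cancels the POD90 call. No section says so, and none says that POD90 is still attempted. The review also has no criteria.
- **A late count is not equivalent.** It is tempting to say that leftovers are fixed once dosing ends, so the data are lost needlessly. That holds only if the participant stopped at POD30 and kept everything, which is least safe to assume in the disengaged. Disposal or later use inflates PDC, and this matters for non-inferiority if it differs between tablets and syringes. Late counts therefore do not belong in the primary analysis.
- **The frequency is unknown.** Section 9.7 expects little missing data. The 18 participants in the enrolment margin are not a loss-to-follow-up allowance. The rate of about 30% Grade 3 complications in Section 10.4 covers the whole first 90 postoperative days and does not measure who is unreachable at POD30.

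The bias also depends on the Section 9.7 rule for missing data. That rule deserves its own attention, but it does not remove the case for collecting what can be collected.

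**Conclusion.** The point holds as a cheap and worthwhile improvement to data collection. The closing rule is out of step with the phone-only requirement and permits avoidable loss of primary-endpoint counts and of POD90 COST, VTE and bleeding data. This rests on applying the study-visit wording of Section 8.2 to the POD30 call, which is natural but not explicit.

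The size cannot be derived from the documents. The power at stake is at most 6 to 7 points, and under 2 points with five losses. The bias is about 2 to 6 points in the illustrated range, and zero if missingness and the PDC of those missing are the same in both arms. The documents do not support saying that data will be lost needlessly, or that the POD90 call is cancelled. They support saying that data may be lost avoidably.

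**What to change.** Reword Section 8.2 along these lines:

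*A missed POD30 call is a missed visit, not discontinuation from the study. At least three attempts are made by telephone; email may be used in addition, to arrange the call. Attempts continue after POD30, and the POD90 call is attempted in every case. Loss to follow-up is declared only after the POD90 attempts have failed.*

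In Sections 7 and 9.3, state a short window around POD30 for counts that enter the primary analysis. The documents give no basis for its length, so the team should fix it without looking at results by arm. If no count was obtained in the window, take a late count at any contact up to and including the POD90 call. Record the date of the last dose and any doses taken or discarded after POD30.

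In Sections 9.3 and 9.7, flag late counts, keep them out of the primary analysis and add them in a sensitivity analysis, reporting their number by arm.

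The cost is protocol wording, a few fields on the call form and a few more calls by existing staff at a contact that is already scheduled. The downside is that late counts are less accurate and tend to overstate adherence, which is why they are flagged and kept to the sensitivity analysis. No dose, schedule or clinical rule changes.
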